- Frequently touched surfaces will be cleaned and disinfected before and after study visits.
- Chairs will be placed at least 6 feet apart to maintain social distance.
- The research space will be regularly cleaned by Facilities Management.

It is possible that people who smoke cigarettes may be at higher risk for COVID-19 (https://www.who.int/news-room/commentaries/detail/smoking-and-covid-19). Accordingly, the following additional measures are proposed during the COVID-19 pandemic:

- The research team will provide a new disposable mask and pair of gloves to each participant for each in-person visit. After that, treatment groups will be held virtually using a video conferencing program, Zoom. Since some participants may not have the appropriate space or technology to join virtually, the research team will give them the option to borrow a tablet study device for 8 weeks.
- If participants do not have access to a private or quiet place to join the weekly group session, they can come to campus and join in a separate room at GSU. They will still be able to use a GSU computer with internet and camera to join the live group sessions.
- Participating in a video conference session presents no more than minimal risk of harm to subjects. The purpose of the video conference is to be able to continue providing the quit smoking group to participants while minimizing the risk of exposure to COVID-19 through elimination of in-person group sessions.

*Strategies for Promoting Engagement with Virtual Group Sessions:

We will use the following strategies to promote engagement:

- Participants in MBAT and MBAT + iQuit will be able to borrow a study tablet for the 8 weeks of the program. This will ensure all participants have equal access to join sessions through the video conferencing software, Zoom.
- Participants will attend an in-person baseline session at GSU, where research staff will help
 them set up Zoom, practice using Zoom, and troubleshoot any issues. Participants will be
 given a packet of Zoom instructions/tips to take with them. For those who will be joining virtual
 sessions from home, study staff will discuss ways to ensure that they have a quiet, private
 location as best as possible. They will also be encouraged to use a virtual background for
 privacy, and study staff will help them set this up.
- Participants will be given the option to join virtual groups in an individual room at GSU. In our
 pilot study virtual sessions, some participants did not have a private place to join. Being able to
 use a tablet in a private room at GSU would provide a solution.
- MBAT participants will attend a group Zoom orientation within two weeks before the first treatment session. This will give them a chance to meet each other, practice using Zoom together (e.g., muting/unmuting, turning camera on and off), and ask questions of the study staff.

- When participants connect to Zoom, study staff will admit them individually into a separate breakout room to ensure that they are in a private location and troubleshoot any issues.
- We will encourage participants to join Zoom sessions a few minutes early so that they have a chance to get to know their fellow group members better.
- Both mindfulness instructors (certified Mindfulness-Based Stress Reduction teachers through the University of Massachusetts Medical School) have experience leading online mindfulness groups through Zoom and will draw on their past experience. For example, they will encourage participants to stay unmuted during discussion to facilitate natural conversation (unless there is excessive background noise); mute participants during mindfulness practices; and provide brief breaks.

*GSU continues to update guidelines for on-campus research. We will follow updated guidelines as they become available.

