4. SELECTION AND ENROLLMENT OF PARTICIPANTS

Participants will include English-speaking adult smokers (ages 18 and above). Recruitment will target a racially/ethnically diverse sample of individuals with relatively low income levels.

Inclusion criteria are:

- at least 18 years of age
- current smoker with history of >3 cigarettes/day (and expired carbon monoxide [CO] >6ppm)
- motivated to guit within next 30 days
- valid home address in the greater Atlanta, GA area
- functioning telephone number
- can speak, read, and write in English

Exclusion criteria are:

- contraindication for nicotine patch or nicotine lozenge
- active substance abuse/dependence or clinically significant depressive symptoms
- current use of tobacco cessation medications
- pregnancy, planning to become pregnant in the next 5 months, or lactation
- household member enrolled in the study
- enrolled in previous smoking cessation study based on mindfulness and/or text messaging at Georgia State University (PI [name] 2017-2020 studies entitled "Mindfulness-based Smoking Cessation Treatment," "Qualitative Study of Text Messages for Smoking Cessation," iQuit iText Study: Feasibility Study of Mindfulness and Text Messaging for Quitting Smoking," or "Evaluation of Mindfulness and Text Messaging for Smoking Cessation")

Recruitment and Enrollment Procedures

Recruitment will focus on flyers; print, radio, and social media; community outreach; and partnerships with local healthcare systems, with targeted recruitment of low-income and racially/ethnically diverse smokers in Atlanta, GA. Study flyers and example social media recruitment advertisements are attached.

Participants will be recruited through flyers (posted at local clinics/community health centers and other community organizations (e.g., YMCA, libraries, non-profit organizations, organizations serving the LGBTQ community, etc.); on and near GSU campuses; in coffee shops, restaurants, and stores selling tobacco products; near MARTA train/bus stops, shelters, etc.) and media (e.g., radio; print media in local newspapers/magazines (both online and paper versions); through GSU digital signage; and on MARTA buses/trains). Participants may also share flyers or the survey link with other individuals who are interested in participating.

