For our previous smoking cessation study at GSU, the inclusion criteria were slightly more rigid. For example, interested individuals were excluded if they also used tobacco products other than cigarettes. Given that use of other tobacco products (e.g., cigars, little cigars, cigarillos) is common among low-income adult smokers, we believe it is important to include these people and help them quit smoking cigarettes as well as other tobacco products. Accordingly, we will contact individuals who expressed interest in our previous smoking cessation study and did not qualify at that time but might meet the current eligibility criteria. We will describe the current study and if they are interested, they will complete the same screening procedures as other potential participants.

Randomization. Randomization will take place at the end of the baseline session, after baseline assessments have been administered. Stratified permutated block randomization will be implemented. Block randomization can achieve balance in the number of assignments to each treatment group. This form of randomization can be conducted within each stratum (i.e., stratified permutated block design) in efforts to achieve both covariate balance and treatment balance. To Given the dangers of overstratification (e.g., with too many strata, there may be insufficient numbers of participants within each block), researchers have recommended using one or two stratification variables that are expected to be most strongly associated with the outcome. To Stratification will be conducted with respect to race/ethnicity and poverty status, both of which are predictors of smoking cessation success.

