- Tobacco History assesses onset of regular smoking, previous quit attempts, abstinence history, smoking rate, and partner smoking status. This includes the Heaviness of Smoking Index comprises two items from the Fagerström Test for Nicotine Dependence (FTND) ²⁹: self-reported average number of cigarettes smoked per day and time to first cigarette upon waking ("time to first cigarette"). The HSI is a strong indicator of nicotine dependence ³⁰.
- Smoking Status (SRNT) surveys tobacco use, use of other tobacco products, and nicotine replacement medications. Smoking Abstinence will be assessed according to the SRNT guidelines ³¹, which suggest reporting point prevalence abstinence (i.e., no smoking during

past week), continuous abstinence (i.e., no smoking since quit date), and time to relapse (i.e., any tobacco use over 7 consecutive days or 2 consecutive weeks). All self-reported abstinence will be biochemically confirmed by CO<6ppm. Use of novel tobacco products (e.g., e-cigarettes and heated tobacco products) will also be assessed. Participants will also indicate which forms of nicotine replacement therapy and/or pharmacotherapy (if any) they used in the past week.

- Additional resources used for smoking cessation will ask participants about various strategies
 for quitting smoking (e.g., acupuncture, hypnosis, other text messaging programs or mobile
 apps). This will allow the researchers to capture resources participants might be using to help
 them quit smoking apart from what they receive in the study.
- The *Brief Wisconsin Dependence Motives Questionnaire*³² is a 37-item measures that yields an overall dependence score and subscale scores for other dimensions (i.e., cognitive enhancement, affective enhancement, automaticity, affiliative attachment, loss of control, craving, cue exposure/associative processes, social/environmental goals, taste/sensory processes, weight control, tolerance).
- The Wisconsin Smoking Withdrawal Scale ³³ includes subscales for anger, anxiety, sadness, concentration difficulty, craving, hunger, and sleep. All subscales have excellent internal consistency and validity.³⁴
- The Self-Efficacy Scale assesses confidence for resisting smoking urges in specific types of situations (e.g., when feeling stressed, when with friends) ³⁵ Subscales include negative affect, pleasure, social image, social influence, and diet. Scores are predictive of relapse. ³⁶

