- Participants will complete *Program Evaluations* to provide for their feedback about and suggestions for improving the intervention (both MBAT and iQuit Mindfully text messages). Usual care participants will answer 1 program evaluation question: "On the scale below, please circle the number that best represents whether you would recommend this quit smoking program (or something similar) for others who are interested in quitting smoking." (rated on 1-10 scale).

The maximum time between telephone screening and enrollment will be 1 month. The maximum time between baseline assessment and start of treatment will be 1 month. However, we will employ a variety of strategies to ensure that these timeframes are as short as possible. For example, in order to reduce the time between telephone screening and baseline we will offer a variety of days and times for baseline assessment. We will also time our recruitment efforts around planned baseline assessments to maximize potential participants' interest (in order to prevent longer wait time to accrue a sufficient number of participants to start a group).

Electronic Diary Assessments. *Electronic Diary Assessments* (also referred to as short-surveys) will be administered in the evening on every other day from Week 2 to Week 8, thus capturing key processes surrounding quitting smoking. Diary assessments will assess smoking behavior ("How many cigarettes did you smoke today?") and each of the hypothesized mechanisms (mindfulness, emotions, craving and withdrawal, self-efficacy, and social support). Participants will also indicate their mindfulness practice that day (See Appendix). Participants will receive an email and/or text with the REDCap link to the electronic diary assessment survey. Both participant-initiated options allow respondents to complete assessments at a time that is convenient to them between that evening and the next morning (by 9am).

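### The trial enrols cigar and cigarillo users on purpose, but the diary smoking item given in the protocol counts only cigarettes, so a switch to cigarillos enters the Aim II diary analysis as not smoking

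*Combined protocol and SAP*

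**What the plan says.** **Who is enrolled.** Section 4 states that "use of other tobacco products (e.g., cigars, little cigars, cigarillos) is common among low-income adult smokers". It contrasts this trial with a previous study at the same university that excluded such users, and says "we believe it is important to include these people and help them quit smoking cigarettes as well as other tobacco products". Every participant must also smoke cigarettes: the entry criterion is "current smoker with history of >3 cigarettes/day (and expired carbon monoxide [CO] >6ppm". The exclusion list does not mention other tobacco.

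**The diary.** Section 6.2 describes an evening diary, "every other day from Week 2 to Week 8". The only smoking question it gives is "How many cigarettes did you smoke today". It refers to an appendix for the diary content.

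**The visit survey.** The schedule in Section 6.1 and the Smoking Status entry in Section 6.2 collect use of other tobacco and electronic vapor products at baseline and at weeks 1, 3, 5, 8, 12 and 24.

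**The outcome wording.** Section 6.2 words relapse as "time to relapse (i.e., any tobacco use over 7 consecutive days or 2 consecutive weeks". Its two abstinence measures are worded differently. The longer one is "continuous abstinence (i.e., no smoking since quit date", and the 7-day one likewise speaks of smoking without naming a product. No passage says which products count as smoking, or how reported use of another product changes a participant's abstinence status.

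**The analysis.** For hypothesis 2b, Section 9 (Aim II) relates negative affect and craving at one assessment to smoking at the following one. It does so with questionnaire data and with diary data, and asks whether the relation is weaker in the mindfulness arms than in usual care.

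**The concern.** The diary item is narrower than the population and the aim. The protocol expects other combusted tobacco to be common in the people it recruits and wants them to stop it, yet the one daily measure of smoking that it shows cannot register it.

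At stake is the diary test of hypothesis 2b. Suppose negative affect or craving leads a participant to smoke a cigarillo rather than a cigarette. The diary then pairs high negative affect with no smoking. That pulls the estimated link towards zero for that person. If such switching were more frequent in one arm than another, the weakening would differ by arm and could imitate, or hide, the attenuation that hypothesis 2b predicts. The documents give no reason to expect a particular direction.

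The same hypothesis is also tested with questionnaire data, which do record other tobacco. The two tests therefore rest on outcomes of different scope, and a disagreement between them would be hard to interpret.

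**Working it through.** There is no sample-size or power figure to reproduce, because the point concerns definitions. The check applies the stated items to defined cases and then traces each definition to the analyses that use it.

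**Step 1: the diary item applied to one day.**

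| Smoked that day | Diary answer | Scored as |
|---|---|---|
| Cigarettes only | Above zero | Smoking, correct |
| Cigarettes and cigarillos | Above zero | Smoking, but amount understated |
| Cigarillos only | Zero | Not smoking, wrong |
| Nothing | Zero | Not smoking, correct |

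The wrong classification is confined to days with other combusted tobacco and no cigarettes. All participants smoke cigarettes at entry, so such days arise mainly when someone cuts out cigarettes but not the other product.

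**Step 2: can the visit survey fill the gap?** Section 5 pays $5 per diary up to $120, so up to 120 / 5 = 24 diaries per participant. The visit surveys inside the week 2 to week 8 window are those at weeks 3, 5 and 8, which makes three. Three surveys can show that a participant used another product. They cannot say on which of 24 days, and the analysis needs the timing.

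**Step 3: the visit definitions.** Take a participant at week 8 who has used one other product daily for at least 7 days and no cigarettes. Self-reported 7-day status depends on what smoking is taken to mean:

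| Product | Cigarettes only | Any combusted | Any tobacco | Relapse wording |
|---|---|---|---|---|
| Cigar or cigarillo | Abstinent, if CO is also <6 ppm | Not abstinent | Not abstinent | Met |
| Smokeless tobacco | Abstinent | Abstinent | Not abstinent | Met |
| E-cigarette | Abstinent | Abstinent | Not abstinent | Met, if it counts as tobacco, as Section 6.2 implies |

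The abstinence and relapse wordings agree for all three products only under the any-tobacco reading, which the text does not state.

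**Step 4: which definitions reach a planned analysis?**
- Diary smoking: yes, in Section 9, Aim II.
- 7-day abstinence: yes. It is the primary outcome at weeks 8, 12 and 24. Lapse recovery also uses smoking status, since that analysis is restricted to people classed as smoking at the last treatment session.
- Continuous abstinence and time to relapse: no. Section 6.2 lists them as measures that a guideline suggests reporting. They are not among the primary or secondary outcomes and have no analysis in Section 9.

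**Step 5: week 24.** Verification changes from CO to saliva cotinine <20 ng/ml. Section 6.2 recognises that non-combusted nicotine can affect cotinine and collects its use, but gives no rule for scoring a participant who reports it.

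**The case against.** The strongest objection is that the diary itself has not been seen. Section 6.2 gives one item in parentheses and points to an appendix that is not among the documents. That appendix may contain a further tobacco question. This stands, and the recommendation is conditional on it. If such an item exists, only a sentence on how it is scored is needed.

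A second objection is that the visit outcomes can be scored under any scope, because other-product use is asked at every assessment. This also stands. For the visits the gap is a missing rule, not missing data. It does not help the diary.

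Three stronger readings are tempting, and the documents do not support them:

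- A reader might infer that a cigarillo user can be abstinent, relapsed and smoke-free at once. Smoking a cigarillo is smoking in plain words. The overlap needs a cigarettes-only reading that no passage states, and CO below 6 ppm as well. It follows more readily for smokeless or e-cigarette users, but the abstinent/relapsed half of it touches no analysis planned in Section 9. The relapse wording also requires sustained use, so an isolated occasion is not relapse.
- A reader might infer that product switching inflates a smoke-free-day result. The plan analyses no rate of smoke-free diary days. The effect is on the association tested under hypothesis 2b.
- A reader might put a size on it. If 15-30% of participants used other combusted tobacco and 10-30% of their diary days after quitting were cigar-only, between 0.15 × 0.10 = 1.5% and 0.30 × 0.30 = 9% of diaries would be wrongly zero. Every input there is an assumption; the documents say only that such use is common.

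**Conclusion.** The concern holds for the diary. As shown in the protocol, the smoking item misses combusted tobacco that the trial expects its participants to use and aims to help them stop. A participant who switches from cigarettes to cigarillos is scored as not smoking in the Aim II diary analysis. The gap cannot be repaired from the visit surveys once the diaries are in.

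The conclusion assumes that the appendix has no other tobacco item. Its size cannot be computed from the documents, and neither can the direction of any bias in the comparison between arms.

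The differing wording of abstinence and relapse is a secondary matter of clarity. The unstated product scope of 7-day abstinence deserves a sentence because that outcome is primary. A combusted-only scope is one of several defensible choices for it: the aim of helping people stop other tobacco products could also support a wider one.

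**What to change.** **Diary.** First check the appendix. If it has no such item, keep the cigarette count unchanged and add one question on how many cigars, little cigars, cigarillos or other combusted tobacco products were smoked that day. In Section 9, define diary smoking as any combusted tobacco.

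**Visit outcomes (secondary).** In Section 6.2, name the products that count as smoking and use the same scope for point prevalence abstinence, continuous abstinence and relapse. State how reported use of another product is scored at each visit. Include week 24, where a participant who uses only non-combusted nicotine may fail the cotinine cut-off. Settle this before outcome data are examined, so that the scope of the primary outcome is not open to choice afterwards.

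**Cost.** One extra diary item and a few sentences of protocol and SAP text; the visit data need no new collection. Diaries completed before the change lack the new item and need a flag. A sensitivity analysis of hypothesis 2b could leave out the flagged diaries of participants who reported other combusted tobacco at any visit survey. Keeping the cigarette count leaves that item comparable across the whole trial.

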Aim II. Investigate the mechanisms through which mindfulness training impacts smoking cessation. Participants will complete questionnaires from baseline through 24 weeks after the start of treatment, in addition to intensive diary assessments for 6 contiguous weeks during treatment. We hypothesize that:

- 2a) Compared to UC, the mindfulness treatment arms (MBAT, iQuit Mindfully, and MBAT + iQuit Mindfully) will increase mindfulness; reduce negative affect (NA) and volatility of NA (i.e., greater affective stability); increase positive affect; reduce craving and withdrawal; and increase self-efficacy and social support, all of which will mediate effects of the mindfulness-based treatment arms vs. UC on abstinence.
- 2b) Compared to UC, MBAT, iQuit Mindfully, and MBAT + iQuit Mindfully will all attenuate links between NA/craving and smoking. That is, in addition to reducing NA and craving (2a), mindfulness training is hypothesized to weaken the relationships between NA/craving and smoking.

2c) Compared to MBAT, MBAT + iQuit Mindfully will produce stronger effects on the above mechanisms (2a, 2b). Mechanisms outlined in 2a will mediate effects of MBAT + iQuit Mindfully vs. MBAT on abstinence.

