6. STUDY PROCEDURES

6.1 Schedule of Treatment Procedures and Evaluations

			Weeks									
	Phone/ Online Screen	Base- line	1 Start of Tx	2	3	4	5	6	7	8 End of Tx	12 (3 Month Follow- Up)	24 (6 Month Follow- Up)
Telephone/Online Screening	Х											
Compensation			\$30		\$30		\$30			\$40	\$60	\$70
Electronic Diary Assessments		Every	other day	surveys 1	from week	2 to wee	k 8; \$5 pe	r survey 1	or up to \$1	20 total		
TREATMENT PROCEDURES												
Virtual MBAT groups (MBAT & MBAT + iQuit Mindfully conditions)			Tx 1	Tx 2	Tx 3	Tx 4	Tx 5	Tx 6	Tx 7	Tx 8		
iQuit Mindfully text messages (iQuit Mindfully & MBAT + iQuit Mindfully conditions)		Text messages based upon participants' choice in frequency and timing of messages										
Self-Help Materials (all conditions)		Χ	X									
Nicotine Replacement Therapy Dispensation (all)			Participants receive 4 weeks of patches and lozenges in person at baseline, and then the remaining 4 weeks of patches are mailed.									
IN-PERSON ELIGIBILITY												
Carbon Monoxide		Х								Х	Х	Х
Cotinine (Saliva Sample)												Х
Screening for Depression and Substance Dependence		Х										
SMOKING												
Information for Setting Up Text Messages		Х										
Tobacco History	Х											
Smoking Status, use of other tobacco products, electronic vapor products, NRT, pharmacotherapy		Х	Х		Х		Х			Х	X	Х

	Phone/ Online Screen	Base- line	1 Start of Tx	2	3	4	5	6	7	8 End of Tx	12 (3 Month Follow- Up)	24 (6 Month Follow- Up)
Additional Resources Used for Smoking Cessation										Х	X	X
Wisconsin Inventory of Smoking Dependence Motives (WISDM)		Х								Х	Х	Х
Wisconsin Smoking Withdrawal Scale (WSWS)			Х		Х		Х			Х	Х	Х
Self-Efficacy Scale		Х	Х		Х		Χ			Х	Х	Х
MINDFULNESS												
Mindfulness Attention Awareness Scale (MAAS)		Х								Х	Х	Х
Five Facet Mindfulness Questionnaire (FFMQ short form)		Х								Х	Х	Х
Mindfulness Practice Frequency					Х		Х			Х	Х	Х
Self-Compassion Scale (short form)		Х								Х	Х	Х
STRESS/ NEGATIVE AFFECT												
Perceived Stress Scale		Х								Х	Х	Х
Positive and Negative Affect Scale		Х	Х		Х		Х			Х	Х	Х
Experiences with Discrimination		Х										
SOCIAL SUPPORT												
Multidimensional Scale of Perceived Social Support			Х							Х	Х	Х
Group Climate Questionnaire (MBAT & MBAT + iQuit Mindfully)										Х		
PROGRAM EVALUATION												
Text Message Feedback					Х		Х				Х	Х
Perceived Benefits										Х	Χ	Х
Program Evaluation Questionnaire										X		

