9. STATISTICAL CONSIDERATIONS AND DATA ANALYSES

We will conduct both intent-to-treat (ITT) and per protocol analyses. ITT includes all participants that were randomized, regardless of compliance, withdrawal, and other events after randomization. A strength of ITT is that it is based on original randomization. However, effect estimation using ITT may be conservative and misleading with increasing attrition. Per protocol analysis considers only participants who fully complied and completed the study. Per protocol is less conservative and may reflect true treatment differences for those with full compliance. Including both approaches will provide a more complete understanding of treatment effects.

Analyses will be performed using SAS. Descriptive statistics for all measurements will be reported. Frequency distributions will be created to screen for any coding or entry errors. Frequency distributions summarize categorical data, and measures of central tendency and dispersion will summarize continuous data. All data will be examined for bivariate relationships with the outcomes and with each other. All analyses will control for demographics (age, gender, race/ethnicity, education level, partner status) and baseline nicotine dependence (cigarettes per day and time to first cigarette). The overall study level of significance will be α =.05.

Aim I. Test the efficacy of a mindfulness-based text messaging program for smoking cessation ("iQuit Mindfully"), both as a standalone intervention and in combination with virtual counseling.

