The relationship between treatment condition and each dichotomous study outcome (smoking cessation, lapse recovery) will be assessed with a generalized linear mixed model (GzLMM) with a Binomial distribution and logit link function. This is an appropriate statistical model with repeated measures data collected over time. ⁴⁴ A 2-level multilevel GzLMM will be specified, with time nested within subject. This approach will properly account for the multilevel data structure. Fixed effects considered in each model will include demographics, baseline nicotine dependence, treatment condition and time as main effects, and a treatment condition by time interaction. Testing of covariance structure will be conducted, and information criteria will be used to assess model fit and selection. Linear contrasts will be built into the analysis to estimate specific comparative effects of all treatment conditions. To test treatment effects on primary smoking cessation outcomes, repeated measures outcomes will be biochemically-confirmed 7-day point prevalence abstinence at weeks 8, 12, and 24. To test treatment effects on lapse recovery, this analysis will also be conducted among participants classified as smoking at the last treatment session. ¹² In addition, gender and race/ethnicity will be assessed as potential moderators of treatment effects.

The moderating effect of poverty status will be examined with the addition of a poverty status by treatment condition interaction into the models described in 1a). This will be tested using both dichotomous (i.e., below vs. at or above federal poverty threshold) and continuous poverty status variables (i.e., depth of poverty as indicated by income-to-poverty ratio and income deficit/surplus) according to U.S. Census guidelines.^{45,46}

Aim II. Investigate the mechanisms through which mindfulness training impacts smoking cessation.

Hypotheses regarding mechanisms will be tested with both traditional questionnaire data (collected from baseline through 24 weeks after the start of treatment) and electronic diary data (collected for 6 continuous weeks during treatment), separately. Mediation testing will be conducted regardless of statistical significance of intervention effects because of statistical, conceptual, and practical reasons for testing mediation in such cases.⁴⁷ Volatility will be calculated using the mean square successive

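### The primary Aim I abstinence model leaves out the baseline self-efficacy score, a pre-randomisation measure that the protocol calls predictive of relapse, and so forgoes a small gain in power

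*Combined protocol and SAP*

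**What the plan says.** Section 9 fixes one covariate list for every analysis. It holds five demographic items and two smoking items, the latter given as "baseline nicotine dependence (cigarettes per day and time to first cigarette". Under Aim I, the same section repeats the list for the mixed logistic model: "Fixed effects considered in each model will include demographics, baseline nicotine dependence, treatment condition and time as main effects", with a condition-by-time interaction. The outcomes are biochemically confirmed 7-day abstinence at weeks 8, 12 and 24. Self-efficacy appears in neither place.

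The schedule in section 6.1 marks the "Self-Efficacy Scale" at baseline and at weeks 1, 3, 5, 8, 12 and 24, with no restriction by arm. Section 4 fixes the order at the baseline visit: "Randomization will take place at the end of the baseline session, after baseline assessments have been administered". In describing the scale, section 6.2 says: "Subscales include negative affect, pleasure, social image, social influence, and diet. Scores are predictive of relapse".

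Section 1, hypothesis 2a, gives self-efficacy a second role, as a mechanism. The mindfulness arms are expected to "increase self-efficacy and social support, all of which will mediate effects of the mindfulness-based treatment arms vs. UC on abstinence".

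**The concern.** A baseline score recorded before randomisation is a valid covariate. If it predicts the outcome, adjusting for it makes the treatment test somewhat more powerful at almost no cost. Here the protocol itself describes the scores as predictive, the data will be in hand for every arm, and the model for the main question does not use them.

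At stake is a modest amount of power in Aim I. That has some value, because the contrasts with usual care are the thinnest part of the design: 145 participants against 50. Naming the covariate in advance also avoids a disputed post hoc adjustment if the arms turn out to differ visibly on this score.

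**Working it through.** **Inputs from the documents (section 9, power paragraph).** 145 per treatment group, 50 in usual care, d = 0.33 (text messaging) and d = 0.35 (mindfulness), two-sided alpha 0.05, 80% power, 20% attrition.

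**Inputs assumed.** The documents do not give the prognostic strength of baseline self-efficacy or a usual-care quit rate. I take an odds ratio (OR) of 1.2 to 2.0 per SD of the score and quit rates of 10% and 20%. The effect size converts as OR = exp(0.33 × π/√3) = 1.82.

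**1. The plan's own figures.** 3 × 145 + 50 = 485, as stated. A simple two-means calculation at d = 0.33 gives 2 × (1.960 + 0.842)²/0.33² ≈ 144, or 145 with the t correction. That is before attrition; 145/0.8 gives 182. The stated 145 is therefore not reproduced by this route with attrition included. That is a separate matter, but it bears on how much power there is to improve.

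**2. Power against usual care as planned.** On the normal scale, the SE of the standardised difference is √(1/145 + 1/50) = 0.164. Then 0.33/0.164 = 2.01, and power is about Φ(2.01 − 1.96) = 52%. At d = 0.35 it is 57%. After 20% attrition (116 vs 40) the figures are 44% and 48%.

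**3. Adding a covariate, normal scale.** Replacing the SD by SD × √(1 − R²), at 145 vs 50 and d = 0.33:

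| Added R² | Power |
|---|---|
| 0 | 52.1% |
| 0.01 | 52.5% |
| 0.05 | 54.2% |
| 0.10 | 56.4% |

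Reaching 80% would need an added R² of about 0.48. This continuous-outcome version is only a guide, because the planned outcome is binary.

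**4. Adding a covariate, logistic model.** Single visit, 145 vs 50, true OR 1.82, one dependence covariate already in the model, 4,000 simulated trials per row. Each cell shows without → with the self-efficacy score. Efficiency is the squared ratio of estimate/SE; in the last row, (0.638/0.413)² ÷ (0.607/0.402)² = 1.05.

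| Usual-care rate | Log-OR per SD (OR) | Mean estimate | Mean SE | Power | Efficiency |
|---|---|---|---|---|---|
| 10% | 0.2 (1.22) | 0.660 → 0.666 | 0.550 → 0.553 | 15.3% → 15.7% | 1.01 |
| 10% | 0.3 (1.35) | 0.683 → 0.695 | 0.549 → 0.554 | 16.9% → 17.4% | 1.02 |
| 10% | 0.5 (1.65) | 0.654 → 0.676 | 0.533 → 0.544 | 16.4% → 17.2% | 1.03 |
| 20% | 0.2 (1.22) | 0.636 → 0.644 | 0.409 → 0.413 | 31.4% → 31.9% | 1.01 |
| 20% | 0.3 (1.35) | 0.616 → 0.629 | 0.406 → 0.411 | 30.2% → 30.6% | 1.02 |
| 20% | 0.5 (1.65) | 0.607 → 0.638 | 0.402 → 0.413 | 29.5% → 31.6% | 1.05 |

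The SE rises slightly with adjustment. The gain comes from the conditional estimate moving further from zero. Power is lower here than in step 2 because a binary outcome at one visit carries less information.

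With stronger assumed prognosis (OR 1.5 to 2.0 per SD, no other covariates), power rose by 0.6-2.6 points at 145 vs 50 and by 0.9-3.2 points at 145 vs 145. A run over OR 1.2 to 2.0 that also adjusted for a dependence measure correlated with self-efficacy gave an efficiency gain of about 1-8% and roughly 0-3 points of power. I take that as the summary range.

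**5. Type I error.** With no treatment effect, the rejection rate in the step 4 setting was 3.2-4.7% without the score and 3.4-4.6% with it. The omission does not inflate it.

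**6. Chance imbalance against the standard error.** The SD of the standardised imbalance is 0.164. For a log-OR of 0.2 to 0.5 per SD, it shifts the treatment log-OR by 0.03 to 0.08 (one SD), against an SE of 0.40 to 0.52. As a share of variance this runs from (0.033/0.521)² = 0.4% to (0.082/0.396)² = 4.3%.

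**The case against.** The case for leaving the plan alone is a fair one.

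- **The plan does not contradict itself.** It pre-specifies five demographic and two dependence covariates and nowhere commits to adjusting for every measured predictor. This stands; the point is an improvement, not the correction of an error.
- **The evidence is one sentence.** It does not say that baseline scores are meant, gives no strength, and does not address value beyond cigarettes per day and time to first cigarette. This stands, and it is why the gain is a range that starts near zero. In the planned model, the existing covariates and a subject-level random effect probably hold it near the low end.
- **Self-efficacy is a mediator.** That rules out adjusting for scores taken after randomisation. It does not rule out the baseline score.
- **Usual care will have few quitters.** At 10-20% of 50, that is 5 to 10 per visit, in a model that already carries many terms. This argues for adding one covariate and no more.
- **There is a stronger candidate.** Section 4 calls poverty status a predictor of cessation and stratifies on it, yet it is not in the section 9 covariate list and enters only with the moderation analysis. True, but that is a separate point.

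**Conclusion.** The omission is real and its consequence is small. Under an assumed OR of 1.2 to 2.0 per SD, adding the score gains about 1-8% in efficiency and about 0-3 points of power. These figures rest on assumed quit rates, the conversion of d to an odds ratio, and single-visit models in place of the full repeated-measures model.

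A reader might go further in four ways that the documents do not support.

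- **That chance imbalance distorts the odds ratios against usual care.** The 95% limit of imbalance is 1.96 × 0.164 = 0.32 SD. At an OR of 1.5 to 2.0 per SD, that would move the treatment odds ratio by a factor of exp(0.32 × ln 1.5) = 1.14 to exp(0.32 × ln 2) = 1.25. This is an extreme under an assumed strength. Imbalance under randomisation is not bias; the standard error and alpha already cover it (steps 5 and 6).
- **That adjustment would rescue the usual-care contrasts.** Their weakness comes from n = 50, and no plausible covariate supplies an R² of 0.48.
- **That the dependence-motives score and expired carbon monoxide belong in the model too.** The documents make no prognostic statement about either.
- **That taking the smoking items at screening, or the content of the imputation model, is a fault.** Section 6.2 caps the interval from telephone screening to enrolment at one month, and nothing shows harm from it. Section 9 already says that missing values are imputed from baseline responses, which largely covers self-efficacy.

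**What to change.** Optional. Before any unblinded analysis, add one sentence to section 9 (the general covariate statement or the Aim I paragraph): the primary Aim I abstinence model also includes the baseline Self-Efficacy Scale total as one continuous covariate. Specify that only the score from the baseline visit is used, since scores from week 1 onwards follow randomisation and serve as Aim II mediators. State how the total is formed, because section 6.2 names only subscales.

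The cost is one sentence and one model degree of freedom, with no new data. If the sponsor prefers to keep the present list, a line saying that it is deliberate would close the point.
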